# 8 STUDY PROCEDURES/EVALUATIONS

## 8.1 Clinical Procedures/Evaluations

#### 8.1.1 Informed Consent

The informed consent form (ICF) will be approved by the reviewing IRB/EC and executed before performing any study-related activities.

Informed consent will be obtained for all subjects participating in the trial before performing any screening assessments. Subjects may withdraw consent at any time. Participation in the trial may be terminated at any time without the subject's consent as determined by the Investigator.

#### 8.1.2 Demographics

Demographic information (date of birth, gender, ethnicity and race) will be recorded on the subject's source documents and eCRF at Screening Visit. Name, address, phone number, and emergency contact information will be documented in the source documents only.

#### 8.1.3 Inclusion/Exclusion Criteria

Eligibility screening of healthy subjects will be completed within 28 days before study drug dosing and will be documented on the subject's source documents and eCRF. Review of inclusion and exclusion criteria will be performed on Day -2 to determine eligibility for admission, on Day -1, before 12-lead ECG, to determine eligibility for enrollment, and on Day 1 pre-dose to confirm the subject remains eligible for dosing.

Screening failures and the reason for failure to meet the study eligibility requirements will be documented in the source documents and entered into the study database.

#### 8.1.4 Medical History

For subjects enrolled in the trial, the medical history (MH) will be obtained by direct interview of the subject and recorded on the subject's source document and eCRF. The MH will capture the subject's current disease processes, past disease processes, history of hospitalization, history of surgery, allergies, and prior medications (see Section 6.6). Subjects will be queried regarding a history of significant medical disorders of the head, eyes, ears, nose, throat (HEENT), mouth, skin, and the cardiovascular, gastrointestinal, renal, urological, nervous, hematological, lymphatic, endocrine, musculoskeletal, and genital/reproductive systems. A history of hearing abnormalities or hearing loss, especially following administration of aminoglycoside antibiotics or other medications, kidney disorders, cardiovascular disorders, including MI and angina, cardiac arrhythmias including Long QT Syndrome (LQTS), syncope due to cardiac arrhythmias or unexplained, psychiatric illness, and substance abuse will be specifically solicited.

DMID Protocol 20-0012	
Apramycin	

Occupational history of exposure to loud noise will be obtained. Family history of hearing loss, especially on the maternal side, renal disorders, and sudden death will be obtained. The MH will be obtained at Screening Visit and updated upon admission to the CTU at check-in (Day -2), on Day -1, and before dosing on Day 1. After start of study drug dosing, any worsening of predosing MH or new symptoms will be evaluated and reported as TEAEs.

## 8.1.5 Physical Examination

A complete PE – except genital, breast, and rectal exams – will be performed at the Screening Visit, check-in visit (Day -2), Day 3, and Day 14 ( $\pm$  3 days) after dosing, or ET Visit, and will assess general appearance, HEENT, heart, lungs, abdomen, skin, musculoskeletal system, and lymph nodes, and a standard neurological exam.

An abbreviated PE will be performed at Day -1. An abbreviated PE differs from a complete PE in that the abdomen and neurological system are not evaluated.

A symptom-directed (focused) PE may be performed before dosing on Day 1 and at any time after dosing on Day 1 to the last visit (Day  $30 \pm 4$  days) for evaluation of TEAEs.

Height and weight will be measured, and BMI calculated, at the Screening Visit. Weight only will be measured on Day -2, and Day 14 ( $\pm$ 3 days), or ET.

Refer to the protocol-specific MOP for further details. The findings of each examination will be recorded on the subject's source documents and eCRF. Any new findings on examination or worsening of existing conditions after dosing are to be reported as TEAEs.

#### 8.1.6 Vital Signs

VS include resting (measured after supine for at least 5 min) systolic blood pressure (SBP) and diastolic BP (DBP), heart rate (HR), respiratory rate (RR) and oral temperature (T). VS will be measured at the Screening Visit, on Day -2, on Day -1, on Day 1 (within 0.5 h [30 min] before dosing and at 0.5 h  $\pm$ 5 min, 1 h  $\pm$ 5 min, 4 h  $\pm$ 10 min, and 16 h  $\pm$ 15 min after dosing); on Day 2 (at 24 h  $\pm$ 1 h and 36 h  $\pm$ 1 h after dosing); on Day 3 (at 48 h  $\pm$ 1 h and 60 h  $\pm$  1 h after dosing); and on Day 14 ( $\pm$  3 days), or ET. Normal references ranges are shown in Appendix B, Table 2, and exceptions for enrollment in Section 5.1, Inclusion Criterion #2.

VS that are considered aberrant due to an error in measurement may be repeated. At Screening and after dosing, an abnormal VS measurement may be repeated up to two more times at rest, within 5 min of each other. If the second measurement is abnormal, it will be reported at the highest grade of the two measurements and the subject will be excluded (if at Screening Visit) or the event reported as a TEAE and graded for severity per Appendix B, Table 2 (if after dosing). If the second measurement is normal, a third measurement will be taken at least after 5 min at rest. If the third measurement is still normal, the subject is eligible (if at Screening Visit) or there is no TEAE (if after dosing); if it is abnormal, the subject will be excluded (if at Screening Visit)

or a TEAE will be reported at the highest assessed grade (between first and third measurements) and graded for severity per Appendix B, Table 2 (if after dosing).

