## 5.1 Subject Inclusion Criteria

All must be answered YES for the subject to be eligible for study participation:

- 1. Subject reads and signs the Informed Consent Form (ICF) and agree to have bronchoscopy with bronchoalveolar lavage under sedation or light anesthesia and comply with study procedures.
- 2. Healthy male or non-pregnant, non-lactating female subjects 18 to 45 years of age (both inclusive) at the time of dosing.
  - a. Note 1: Determined by medical history (MH), medication use, physical examination (PE), and vital signs, clinical laboratory tests and 12-lead ECG within reference ranges at Screening and Day-2. (See Sections 8.1 and 8.2, Appendix B, Table 2, Table 3 and Table 4 and the study-specific MOP.)

Exceptions to BP, HR and laboratory test values being with normal ranges are:

- Abnormal HR and BP on first measurement may be repeated twice more with the subject resting between measurements for at least 5 min according to Section 8.1.6.
- Subjects with baseline  $HR \ge 45$  to 50 bpm may be accepted if otherwise healthy adults with known history of asymptomatic bradycardia.
- Subjects with baseline SBP up to 140 mmHg and DBP up to 90 mmHg may be accepted if otherwise healthy.
- A laboratory value that is Grade 1 will be allowed if not considered to be clinically significant by the investigator, with the exception of ALT, AST, AP, BUN, urine protein, serum creatinine or estimated glomerular filtration rate (eGFR) <70 mL/min /1.73 m^2 by the Chronic Kidney Disease Epidemiology collaboration (CKD-EPI) equation.
- 3. Female subjects of childbearing potential should use highly effective methods of contraception from the time of screening to 30 days after dosing.
  - Note 1: A female is considered of childbearing potential unless post-menopausal (defined as history of ≥1 year of spontaneous amenorrhea and a FSH level >40 IU/L), or permanently surgically sterilized.

- Note 2: Highly effective contraceptive methods include: (a) surgical sterilization methods, such as tubal ligation, bilateral oophorectomy, salpingectomy, hysterectomy, or successful tubal obliteration (e.g., Essure®) with documented radiological confirmation test at least 90 days after the procedure, or (b) long-acting reversible contraception, such as progestin-releasing subdermal implants, copper intrauterine devices (IUDs), levonorgestrel-releasing IUDs.

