## 9.2 Methods and Timing for Assessing, Recording, and Analyzing Safety Parameters

#### 9.2.1 Adverse Events

#### Definitions

ICH E6 defines an AE as any untoward medical occurrence in a subject or clinical investigation subject who was administered a pharmaceutical product, regardless of its causal relationship to the product. An AE can therefore be any unfavorable and unintended sign (including an abnormal laboratory finding), symptom, or disease temporally associated with use of the product,

DMID Protocol 20-0012	Version 5.0
Apramycin	10 July 2023

and are described as treatment-emergent AEs (TEAEs). The occurrence of a TEAE may come to the attention of study personnel during study visits and interviews, or by a subject presenting for medical care.

The FDA defines an AE as any untoward medical occurrence associated with the use of a drug in humans, whether it is considered drug-related or not.

Any systemic medical condition, VS and ECG measurement, and clinical safety lab test value that is present on Day 1 prior to dosing will be considered a baseline finding for the purpose of data analysis. For ear and otoacoustic testing, baseline comprises assessments performed on Day -2. However, if the condition increases in severity or frequency after IMP administration at any time during the trial, it will be recorded as a TEAE.

Any medical condition that is reported after screening but before study drug administration will be evaluated and reported as MH update.

All TEAEs will be graded for severity according to Appendix B, Table 2, Table 3, and Table 4 and for relationship to the study drug.

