#### 9.2.3 Procedures to be Followed in the Event of Abnormal Laboratory Test Values or Abnormal Clinical Findings

A licensed study clinician (listed on FDA Form 1572) will determine seriousness, severity, and causality of abnormal laboratory values; provide a medical evaluation of TEAEs; and classify TEAEs based upon medical judgment.

Abnormal laboratory values or clinical findings for all enrolled subjects after dosing will be assessed using the toxicity scales in Appendix B. Out of range values and findings noted at screening or baseline, but allowable for enrollment and dosing if within Grade 1, will only be considered TEAEs if their severity increases to Grade 2 or higher. For abnormalities noted from the time of study drug dosing, any Grade 1 or higher laboratory abnormality listed on the toxicity Table 3 in Appendix B will be entered in the database as a TEAE. Safety laboratory results that are reported as TEAEs will be evaluated by the CTU clinician as clinically significant (CS) or not clinically significant (NCS). Abnormal laboratory values, performed as part of HEM, COAG, CHEM, or UA but not listed in this toxicity table will be evaluated by the study clinicians, recorded in the source document and, if clinically significant, considered TEAEs and graded according to the criteria in Section 9.2.1.

Protocol-specific laboratory normal range values are included in the study-specific MOP and toxicity grades for evaluation of TEAEs are included in Appendix B, Table 3.

Gross blood in urine that is confirmed due to menses is not a TEAE (but is for all other reasons).

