#### **COMMENTS REGARDING THE USE OF THESE TABLES**

- Standardized and commonly used toxicity tables (Division of AIDS, National Cancer Institute [NCI] Common Toxicity Criteria [CTC], and World Health Organization [WHO]) have been adapted for use by the Division of Microbiology and Infectious Diseases (DMID) and modified to better meet the needs of subjects in DMID trials.
- For parameters not included in the following Toxicity Tables, the CTU will refer to the "Guide for Estimating Severity Grade" located above.
- Criteria are generally grouped by body system.

Some protocols may have additional protocol specific grading criteria, which will supersede the use of these tables for specified criteria.

Clinical AEs	Reference range	Mild (Grade 1)	Moderate (Grade 2)	Severe (Grade 3)
VITAL SIGNS 				
Fever - °C	36.1 - 37.2 	37.3 - 38.4	38.5 - 38.9	>38.9
Fever - °F	97.0 - 99.0 	99.1 - 101.1	101.2 - 102.0	>102.0
Tachycardia - bpm	50 - 100 	101 - 115	116 - 130	>130 or ventricular dysrhythmias
Bradycardia – bpm		45 - 49	40 - 44	<40
Hypertension (systolic) - mmHg	130/89 2,3,4,5	131 - 150	151 - 160	>160
Hypertension (diastolic) - mmHg		90 - 95	96 - 100	>100
Hypotension (systolic) - mmHg		85 - 88	80 - 84	<80
Tachypnea – breaths per min	10 - 20 	21 - 25	26 - 30	>30

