### 14.3.4 Abnormal Laboratory Value Listings (by Participant)

### Table 23: Listing of Abnormal Laboratory Results – Chemistry

[Implementation Note: This listing is included in the table shells document, as it is included in the body of the CSR. This listing includes all abnormal Chemistry results (laboratory results outside of the normal range defined in the protocol). Normal chemistry results for other parameters that occurred on the same visit as the abnormal result will not be listed. Results that are outside the normal range but not mild, moderate, or severe will have "(ONR)" included after the result. Similarly, results that meet grading criteria of mild, moderate, or severe but which are not treatment emergent (not worse than baseline) will be shown as ONR. Listing should be sorted by Cohort, Participant ID, Timepoint, and Parameter.]

Cohort	Participant ID	Sex	Age (years)	Planned Study Day	Actual Study Day	Laboratory Parameter (Units)	Result (Severity)	Clinical Significance	Relationship to Treatment	If Not Related, Alternate Etiology	Action Taken with Study Treatment	Participant Discontinued Due to Result?

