# Table 50:Kidney Function Biomarker Summary Statistics Measurement and Change from
Baseline by Parameter and Timepoint – Safety Subset Population

### 14.3.6 Displays of Vital Signs

### Table 51: Vital Sign Toxicity Grade by Parameter, Timepoint, and Severity – Safety Population

[Implementation Note: If there is not at least one mild, moderate, or severe result with a parameter, then only the "Baseline" and "Maximum Severity Post Baseline" rows will be shown for that parameter. Toxicities representing an increase in the laboratory result will be summarized separately from decreases.]

			Mi Gra	ild / ide 1	Mod Gra	erate/ ide 2	Sev Gra	ere/ de 3
Parameter	Time Point	Ν	n	%	n	%	n	%
Any Parameter	Baseline	x	х	XX	х	XX	x	XX
	Maximum Severity Post Baseline	x	х	XX	х	XX	x	XX
	Day 1, 0.5 h Post-Dose	x	х	XX	х	XX	x	XX
	Day 1, 1 h Post-Dose	x	х	XX	х	XX	x	XX
	Day 1, 4 h Post-Dose	x	х	XX	х	XX	x	XX
	Day 1, 16 h Post-Dose	x	х	xx	х	XX	x	XX
	Day 2, 24 h Post-Dose	x	х	XX	х	XX	х	XX
	Day 2, 36 h Post-Dose	x	х	XX	х	XX	х	XX
	Day 3, 48 h Post-Dose	x	х	XX	х	XX	х	XX
	Day 3, 60 h Post-Dose	x	х	xx	х	XX	x	XX
	Day 14	x	х	XX	х	XX	х	XX
Systolic Blood Pressure, Decrease	Baseline	x	х	XX	х	XX	х	XX
	Maximum Severity Post Baseline	x	х	xx	х	XX	x	XX
		x	х	XX	х	XX	х	XX
		x	х	XX	х	XX	x	XX

Notes: N = Number of participants in the Safety Population with the vital sign assessed at the respective timepoint. Baseline = The most recent measurement prior to start of infusion. The "Maximum Severity Post Baseline" rows indicate the maximum severity experienced by each participant at any time point post baseline, including unscheduled assessments.

Table with similar format:

Table 52:Vital Sign Toxicity Grade by Parameter, Timepoint, and Severity – Safety Subset
Population

				Measu	rement			Change fr	om Baseline	
Parameter	Timepoint	Ν	Mean	SD	Median	Min, Max	Mean	SD	Median	Min, Max
Systolic Blood Pressure (mmHg)	Baseline	х	XX.X	XX.X	XX.X	xx, xx	-	-	-	-
	Day 1, 0.5 h Post-Dose	х	XX.X	XX.X	XX.X	xx, xx	XX.X	XX.X	XX.X	xx, xx
	Day 1, 1 h Post-Dose	х	XX.X	XX.X	XX.X	xx, xx	XX.X	XX.X	XX.X	xx, xx
	Day 1, 4 h Post-Dose	х	XX.X	XX.X	XX.X	xx, xx	XX.X	XX.X	XX.X	xx, xx
	Day 1, 16 h Post-Dose	х	XX.X	XX.X	XX.X	xx, xx	XX.X	XX.X	XX.X	xx, xx
	Day 2, 24 h Post-Dose	х	XX.X	XX.X	XX.X	xx, xx	XX.X	XX.X	XX.X	xx, xx
	Day 2, 36 h Post-Dose	x	XX.X	XX.X	XX.X	xx, xx	XX.X	XX.X	XX.X	xx, xx
	Day 3, 48 h Post-Dose	х	XX.X	XX.X	XX.X	xx, xx	XX.X	XX.X	XX.X	xx, xx

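### Protocol 8.1.6 makes a repeated abnormal post-dose vital sign a TEAE with no baseline condition, contradicting 9.2.1 and 9.2.3, although entry accepts values already in the Grade 1 band

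*Protocol*

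**What the plan says.** **Entry.** Protocol 5.1, criterion 2, lists exceptions to the normal ranges: "Subjects with baseline SBP up to 140 mmHg and DBP up to 90 mmHg may be accepted if otherwise healthy", and a heart rate from 45 "to 50 bpm may be accepted if otherwise healthy adults with known history of asymptomatic bradycardia".

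**Grading.** In Appendix B, Table 2, the row "Hypertension (systolic) - mmHg" puts Grade 1 at 131 to 150 and Grade 2 at 151 to 160. Grade 1 is 90 to 95 for diastolic hypertension (Grade 2 from 96) and 45 to 49 for bradycardia (Grade 2 is 40 to 44).

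**Post-dose rule.** Section 8.1.6 allows up to two repeats. If the second reading is abnormal, the instruction is "the event reported as a TEAE and graded for severity per Appendix B, Table 2 (if after dosing"). If the second is normal and the third abnormal, it is also a TEAE. There is no TEAE only when the second and third are both normal. Baseline is not mentioned.

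**Baseline rules elsewhere.**
- Section 9.2.1 covers "Any systemic medical condition, VS and ECG measurement, and clinical safety lab test value that is present on Day 1 prior to dosing" and treats it as a baseline finding, to be recorded as a TEAE if it increases in severity or frequency.
- Section 9.2.3 says out-of-range values and findings at screening or baseline that were allowable within Grade 1 "will only be considered TEAEs if their severity increases to Grade 2 or higher".
- SAP section 9 says a medical condition present at screening is not an AE unless it worsens. SAP 9.6 restates the Grade 2 rule for laboratory results. SAP 9.7, on vital signs, has no equivalent.

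**Confirmation.** Table 2, Note 2 asks for at least three measurements with two concordant before a vital-sign TEAE.

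**The concern.** Section 8.1.6 is the vital-sign procedure that site staff will follow at each timepoint. It decides TEAE status from repeats taken minutes apart. Those confirm that a reading is real, but not that it differs from the subject's value before dosing. A subject admitted under the blood pressure or heart rate exception can therefore become a TEAE without having changed.

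No order of precedence is stated between 8.1.6 and section 9.2, so the outcome depends on which text the site applies. TEAE incidence and vital-sign changes are secondary outcomes (Protocol 3.2.2). There is no control arm against which a background rate of mild events could be judged.

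**Working it through.** The plan gives no TEAE rate or blood pressure variability, so there is no figure of its own to reproduce.

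**1. Overlap of accepted values with Grade 1**
- SBP: accepted to 140, Grade 1 from 131, so 131 to 140 (10 integer values).
- DBP: accepted to 90, Grade 1 from 90, so 90 only (1 value).
- HR: accepted from 45, Grade 1 is 45 to 49, so 45 to 49 (5 values).

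**2. One record under each rule** (pre-dose SBP 134; 4 h readings 135 and 133)
- 8.1.6: both readings exceed 130, so TEAE.
- 9.2.1: Grade 1 before and after, so severity has not increased and this is not a TEAE on severity. Frequency is not defined for a repeated measurement.
- 9.2.3: 135 is below the Grade 2 floor of 151, so not a TEAE.

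For a subject whose SBP stays constant at 131, 135 or 140, the probability of a TEAE is 1.00 under 8.1.6 alone and 0.00 under 9.2.3. The same holds for a constant DBP of 90 and a constant HR of 45 to 49.

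**3. The two baseline rules against each other**
- Reference time: Day 1 pre-dose (9.2.1) against screening or baseline (9.2.3).
- Threshold: any increase in severity or frequency (9.2.1) against Grade 2 or higher (9.2.3).
- A subject who is Grade 1 at Screening, normal before dosing on Day 1 and Grade 1 at 4 h is a TEAE under 9.2.1 but not under 9.2.3.

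**4. Number of readings.** 8.1.6 stops at two when both are abnormal; Note 2 wants at least three. If concordant means two abnormal readings, the classification is the same and only the procedure differs. If it means two readings of the same grade, the classification can differ. The documents do not say which.

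**5. Size, SBP only, no drug effect.** Assumptions not in the documents: mean 120, between-subject SD 10, visit SD 6, within-sitting SD 4 mmHg. Subjects enter if SBP is at most 140 at Screening and Day -2. There is one Day 1 pre-dose reading, then nine post-dose timepoints (0.5, 1, 4, 16, 24, 36, 48 and 60 h, and Day 14) with the 8.1.6 repeats; 300,000 simulated subjects per scenario. Under 9.2.3, Grade 1 at Screening, Day -2 or Day 1 counts as pre-existing.

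| Rule | Central case | Range over scenarios |
|---|---|---|
| 8.1.6 as written | 39% | 23% to 55% |
| Grade above Day 1 pre-dose grade | 28% | 18% to 41% |
| 9.2.3 | 18% | 13% to 29% |

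The range runs from mean 115, SD 9, visit SD 6 to mean 122, SD 10, visit SD 8. In 20 participants the central differences are (0.39 − 0.28) × 20 = 2.2 and (0.39 − 0.18) × 20 = 4.2.

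**The case against.** The strongest reply is that the protocol does contain a baseline comparison. Section 9.2.1 names vital signs, 9.2.3 covers values accepted at Grade 1, and SAP section 9 states the worsening principle. Section 8.1.6 can then be read as the way to confirm a measurement, with 9.2 defining what counts as a TEAE. This stands in part. A reader might infer from 8.1.6 that the protocol has no baseline comparison and that unchanged subjects will necessarily be counted; the documents do not support that. But 8.1.6 goes beyond confirmation. It says when there is a TEAE and when there is not, and it does not point to 9.2.

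A reader might also infer that SAP Tables 51 and 52 repeat the fault, because their maximum-severity "rows indicate the maximum severity experienced by each participant at any time point post baseline, including unscheduled assessments", whereas the chemistry listing says "results that meet grading criteria of mild, moderate, or severe but which are not treatment emergent (not worse than baseline) will be shown as ONR". That does not follow. Tables 51 and 52 show graded results, not TEAEs, and they print a Baseline row. The chemistry, ECG and audiometry grade tables (29, 59 and 71) use the same definition. Change from baseline is reported separately in Tables 53 and 54.

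Three limits on the size also stand:
- Every mean and SD is assumed, and Table 2, Note 4(b) restricts who may enter with SBP up to 140, which would thin the 131 to 140 group.
- In the central case only about 15% of participants are Grade 1 pre-dose. About two-thirds of the 8.1.6 events (26 of 39.5 percentage points) arise in participants with a normal Day 1 reading, and a Day 1 rule would keep those.
- The larger difference, about 4 of 20, is against 9.2.3. Against a Day 1 grade rule it is about 2 of 20.

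**Conclusion.** This is an internal contradiction, and it is minor. Read literally, 8.1.6 makes an unchanged subject accepted in the Grade 1 band a TEAE, which 9.2.3 excludes outright and 9.2.1 excludes unless frequency is held to have increased. Those two rules disagree with each other on reference time and threshold, and the number of confirming readings differs between 8.1.6 and Table 2, Note 2.

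The overlap and the contradiction follow from the documents alone. The estimate that the choice of rule moves about 2 to 4 of 20 participants for SBP rests wholly on assumed variability and should be read as an order of magnitude.

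The consequence is confined to the count of mild vital-sign TEAEs. The primary outcomes are pharmacokinetic and no hypothesis is tested. Table 2, Note 5 keeps isolated vital-sign abnormalities out of the halting criteria, and the systemic halting criterion based on graded TEAEs (9.5.1) requires related events of Grade 2 or higher.

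**What to change.** - **Protocol 8.1.6:** add one sentence making a repeated abnormal post-dose vital sign a TEAE only when it has worsened from baseline, under a single named reference time and threshold. The sponsor should choose which existing rule governs; this review does not choose between them.
- **Protocol 9.2.1, 9.2.3 and Table 2, Note 2:** reconcile them with that sentence, including what an increase in frequency means for a repeated measurement and how many readings confirm an event.
- **SAP 9.7:** restate the chosen rule for vital signs, as SAP 9.6 does for laboratory results.
- Leave Tables 51 and 52 as they are, and keep every reading in Listing 17.

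The cost is a few sentences. The downside is that fewer mild vital-sign events are counted as TEAEs; none is lost from the listings.
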